#### **6.6.1.4. Special individual Adverse Reaction Rules**

Dosing in an individual participant will be suspended if they experience any of the following:

- Liver function test elevation
  - ALT or AST value  $> 3 \times \text{ULN}$  in the presence or absence of symptoms. Grade 2 or higher by NCI CTCAE v 5.0.
  - Any possible Hy's law case will be considered a serious adverse event defined as  $\text{ALT} \geq 3 \times \text{ULN}$  AND total bilirubin  $\geq 2 \times \text{ULN}$  (or 35% increase in direct bilirubin) or  $\text{INR} > 1.5$  (if measured)

- Any ALT or AST or other liver function test elevation or trend in elevation that in the opinion of the Investigator and/or Alexion may place the participant at risk if dosing is continued
- Hematology
  - Hemoglobin reduction to an absolute value of 9.5 g/dL (95 g/L) or lower. Because of the repeated blood draws in the study, an addition 0.5 g/dL (5 g/L) over the Grade 2 CTCAE v 5.0 value may be tolerated at the investigator discretion and based on clinical judgment.
  - Platelet count reduction to an absolute value < 75,000/mm^3, defined as Grade 2 or higher by NCI CTCAE v 5.0
  - Any hematologic abnormality that in the opinion of the investigator and Alexion may place the participant at risk if dosing is continued
- QT interval prolongation
  - A prolongation of the QTcF interval of > 500 ms (using consistent, technically valid triplicate ECG)

#### **6.6.1.5. Special group Adverse Reaction Rules**

- For special group adverse reaction stopping rules (ie transaminase elevation, hematologic abnormalities and QT prolongation), dosing will be suspended for all participants or to the dosing group if any of the following occurs:
  - One or more participants experience a non-serious, severe (NCI CTCAE Grade 3) or higher adverse reaction.
  - One or more participants experience a serious adverse reaction, irrespective of severity/CTCAE grade
  - One or more participants experience a Grade 2 or higher adverse reaction that is considered by the SRC of significant medical consequence to the remaining group to require discontinuation of dosing to the remainder of the group

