### **6.6.1. Adverse Reaction Rules**

An adverse reaction is any treatment emergent adverse event (TEAE) that is considered related to the study medication (for a full definition of related TEAEs, see [Section 10.3.3](#)). When a TEAE occurs, timely determination of relatedness is not always feasible. In such cases, the

Investigator and Alexion should use judgment in protecting the individual patient and study population.

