#### **6.6.1.1. General Adverse Reaction Rules**

The general adverse reaction rules refer to all adverse reactions, excluding those relating to the liver and hematology and QT interval prolongation. The Common Terminology Criteria for Adverse Events (CTCAE) may not give clear enough guidance, and grading may not be appropriate for this study in healthy volunteers; therefore, special study-specific rules have been created.

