#### **6.6.1.2. Individual Adverse Reaction Rules**

An individual participant will not receive any further dose(s) of ALXN1840, if either of the following occurs:

- Participant experiences any CTCAE Grade 3 (or higher) adverse reaction, or a serious adverse reaction, irrespective of severity/CTCAE grade.
- Participant experiences any CTCAE Grade 1 or 2 adverse reaction considered to be related to ALXN1840 and considered a safety concern by the SRC.

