#### **6.6.1.3. Group Adverse Reaction Rules**

Dosing will be suspended for all participants or potentially only in an affected dose group (in the event a dose reduction is employed for the second group), if either of the following occurs:

- One participant experiences a non-serious, severe (CTCAE Grade 3) adverse reaction.
- One participant experiences a serious adverse reaction, irrespective of severity/CTCAE grade.
- One participant experiences a Grade 2 or higher adverse reaction which is considered by the SRC of significant medical consequence to the remaining group to require discontinuation of dosing to the remainder of the group

In the event of suspension of dosing, continuation of the study will require a protocol amendment that has been approved by the MHRA and ethics committee.

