#### **6.6.1.6. Safety Oversight and Implementation Stopping Rules**

- If one or more participants fulfill criteria from either the individual adverse reaction rules (outlined in Section 6.6.1.2 and/or Section 6.6.1.4) or for group adverse reaction rules (outlined in Section 6.6.1.3 and/or Section 6.6.1.5), a SRC meeting will be arranged. At this meeting, a decision will be made regarding the continuation/discontinuation of dosing for the remaining participants as well as need for dose modification. Based on the severity and medical risk to other participants and on request of either the Investigator or Alexion, dosing for all participants will be temporarily suspended until the SRC meets.
- The SRC will meet following completion of Day 18 of Group 1 to confirm adequate safety to complete dosing at 30 mg/day. Dose reduction to 15 mg/day may be made

following review of Group 1 data if there is evidence of over-decuppering as determined by AEs and/or ceruloplasmin concentration.

- The SRC will be comprised of, at minimum, the Investigator and Alexion's Medical Monitor. Additional site staff and Alexion personnel may also be included and will be responsible for reviewing all safety data and making determination around dosing.
- In the event of suspension of dosing, continuation of the study will require a protocol amendment that has been approved by the MHRA and ethics committee.

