## 7. DISCONTINUATION OF STUDY INTERVENTION AND PARTICIPANT DISCONTINUATION/WITHDRAWAL

### 7.1. Discontinuation of Study Intervention

In rare instances, it may be necessary for a participant to permanently discontinue (definitive discontinuation) the study intervention. If the study intervention is definitively discontinued, the participant should remain in the study to be evaluated for safety follow-up. See the SoA for data to be collected at the time of discontinuation of study intervention and follow-up and for any further evaluations that need to be completed.

Discontinuation of study intervention for abnormal liver function should be considered by the investigator when a participant meets one of the conditions outlined in the Dose Modification criteria ([Section 6.6](#)) or if the Investigator believes that it is in best interest of the participant.

If a clinically significant finding is identified (including, but not limited to changes from baseline in QT interval corrected using Fridericia's formula [QTcF]) after enrollment, the Investigator or qualified designee will determine if the participant can continue in the study and if any change in participant management is needed. This review of the ECG printed at the time of collection must be documented. Any new clinically relevant finding should be reported as an AE.

Participants must be considered for discontinuation from intervention if any of the following occur during the study:

- Serious hypersensitivity reaction;
- Severe uncontrolled infection;
- Use of disallowed medication;
- Pregnancy or planned pregnancy (see [Section 8.2.6](#)); or
- Alexion or the Investigator deems it is necessary for the participant.

See the SoA ([Table 1](#)) for samples and data to be collected at the time of study intervention discontinuation and follow-up and for any further evaluations that need to be completed.

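### Section 6.6.1.1 takes all liver reactions out of the general stopping rules but 6.6.1.5 restores only transaminase elevation, so a Grade 3 or serious liver reaction without it meets no mandatory stop

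*Protocol*

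**What the plan says.** The stopping rules are in Protocol Section 6.6.1. Section 6.6.1.1 sets the scope of the general rules: "The general adverse reaction rules refer to all adverse reactions, excluding those relating to the liver and hematology and QT interval prolongation". It contains no stopping rule itself. The general rules are the two sections that follow.

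- 6.6.1.2 ends dosing for an individual if: "Participant experiences any CTCAE Grade 3 (or higher) adverse reaction, or a serious adverse reaction, irrespective of severity/CTCAE grade".
- 6.6.1.3 suspends all participants, or the affected dose group, if: "One participant experiences a non-serious, severe (CTCAE Grade 3) adverse reaction". A single serious adverse reaction does the same.

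Two further sections deal with the classes that were taken out.

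- 6.6.1.4 suspends an individual on fixed liver criteria (ALT or AST above 3 x ULN; a possible Hy's law case), on fixed hematology and QTcF criteria, and on an opinion-based liver criterion: "Any ALT or AST or other liver function test elevation or trend in elevation that in the opinion of the Investigator and/or Alexion" may put the participant at risk.
- 6.6.1.5 sets the group stops: "For special group adverse reaction stopping rules (ie transaminase elevation, hematologic abnormalities and QT prolongation), dosing will be suspended for all participants", or for the dosing group, on one Grade 3 or higher reaction, one serious reaction, or a Grade 2 or higher reaction that the SRC judges significant for the rest of the group.

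Section 6.6.1.6 requires an SRC meeting when any individual or group criterion is met, and adds that, depending on severity and risk, "on request of either the Investigator or Alexion, dosing for all participants will be temporarily suspended until the SRC meets".

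**The concern.** A scheme that removes three classes from the general rules and treats them separately works only if the special rules take back everything that was removed. For hematology and QT they do. For the liver, the class removed is wider than the class taken back.

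What falls between the two is a related liver reaction that is Grade 3 or higher, or serious, with no transaminase elevation. For that reaction, whether the affected participant and the others stop would rest on someone's judgment or request. For a reaction of the same grade in any other organ, a fixed rule decides. The protocol describes this as the first repeat-dose study in healthy participants, and Section 2.3.1 states that they get no direct benefit. That is the setting in which fixed stops are most useful.

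**Working it through.** No arithmetic decides this point, and the plan gives no figure to reproduce. The check is to follow one reaction through the rules in order. Take a drug-related liver reaction, Grade 3 or serious, with ALT and AST not elevated (for example isolated bilirubin, GGT or ALP).

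**Provisions that impose a stop by fixed rule**

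| Section | What it requires | Applies here? |
|---|---|---|
| 6.6.1.2 (individual) | Grade 3 or higher, or serious | No: liver reactions are excluded by 6.6.1.1 |
| 6.6.1.3 (group) | One Grade 3 or one serious reaction | No: same exclusion |
| 6.6.1.4, ALT/AST criterion | ALT or AST > 3 x ULN | No: needs a raised transaminase |
| 6.6.1.4, Hy's law criterion | ALT >= 3 x ULN with bilirubin or INR | No: needs raised ALT |
| 6.6.1.5 (group) | Grade 3 or higher, or serious, within the listed classes | No: the liver is listed only as transaminase elevation, after *ie* rather than *eg* |

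Two readings that might close the gap need checking.

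- The word *any* in 6.6.1.2 could be taken to include the liver. The exclusion in 6.6.1.1 would then exclude nothing.
- The Hy's law bullet ends with an INR condition that could be read as standing alone. The note to Table 7 (Section 10.2) pairs INR > 1.5 with ALT >= 3 x ULN. Even read alone, it would stop only the individual.

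**Where the gap ends.** Section 6.6.1.5 puts no multiple of ULN on transaminase elevation, so a reaction with only mildly raised ALT or AST is arguably covered. Hy's law cases are covered.

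**Provisions that act through judgment**

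- 6.6.1.4, opinion-based bullet: the Investigator or the sponsor can invoke it for any liver test. Individual suspension then follows. Under 6.6.1.6 an SRC meeting must be arranged, and that meeting decides on dosing for the remaining participants.
- 6.6.1.6: suspension of everyone until the SRC meets, on request.
- 6.6.1: where relatedness cannot be settled in time, the "Investigator and Alexion should use judgment in protecting the individual patient and study population".
- 6.6: abnormal tests are to be repeated, if necessary daily. The sponsor should be told within 24 hours of a finding of clinical concern, and a decision to discontinue should not wait for causality assessment.
- 7.1: "Discontinuation of study intervention for abnormal liver function should be considered by the investigator". Section 8: immediate safety concerns are to be discussed with the sponsor.
- 4.1 and 9.7: SRC review of Group 1 safety data through Day 18 before Group 2 starts.

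So as written there are several ways to stop, but none is a fixed rule for this reaction.

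**Evidence of intent.** Sections 6.6.1.1, 6.6.1.4 and 6.6.1.5 name the same three classes in the same order. The liver item in 6.6.1.4 has the broad label of liver function test elevation. The note to Table 7 sends the reader to 6.6.1.5 for liver chemistry stopping criteria generally. All of this suggests that 6.6.1.5 was meant to cover the liver as a whole.

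**The case against.** The strongest reply is that the parenthesis in 6.6.1.5 is shorthand. Read with the neighbouring sections and the Table 7 note, it covers the liver, and no site would read it otherwise. As an account of intent this is probably right. It does not make the text correct: the sentence is an operative safety rule, and its stated scope is narrower than the exclusion that it is meant to mirror.

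A second reply is that the narrower scope was chosen. Table 3 describes the liver risk as dose-dependent ALT and AST elevation, and 6.6.1.1 says that CTCAE grading may not suit healthy volunteers. Neither plausibly shows a decision to exempt a serious liver reaction, and 6.6.1.5 itself uses CTCAE grades.

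A third reply is that the safeguards suffice and the case is remote. Much of this stands. The opinion-based bullet in 6.6.1.4 reaches other participants through the mandatory SRC meeting. Amendment 1 records that the MHRA wanted suspension of all participants, pending that meeting, to be clear once a criterion is met; the current text keeps the request condition, so this shows intent only. Bilirubin above ULN and Gilbert's are excluded at entry. Section 6.6 describes the reported GGT elevations as asymptomatic and names them together with transaminases.

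A reader might infer that participants with a severe liver reaction would be left on drug, or that liver injury in general escapes the rules. The documents support neither. Transaminase elevations and Hy's law cases are covered, and continued dosing in the uncovered case would require both the Investigator and the sponsor to decline to act.

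**Conclusion.** The point holds as a scope mismatch in the text. On a literal reading, a related Grade 3 or serious liver reaction without transaminase elevation triggers no mandatory suspension of the individual or the group, whereas the same grade in any other organ suspends the group. It is probably unintended and should be corrected; it is not evidence that the study is unsafe.

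Its size cannot be expressed as a risk, because the documents give no rate for such a reaction. The only figures available count others who could be on drug at the time. In Group 1 this is 6 to 8 less the one affected, so 5 to 7. In a single second group it is 17 - 8 = 9 to 17 - 6 = 11, less one, so at most 8 to 10. These count people dosed, not people expected to be harmed, and they assume about 17 enrolled, nobody dropping out and the group dosed together.

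The conclusion rests on two readings: that the general rules mean 6.6.1.2 and 6.6.1.3, and that *ie* introduces a complete list.

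**What to change.** In 6.6.1.5, replace *transaminase elevation* with *liver-related adverse reactions, including liver function test elevation*. Keep the existing triggers: Grade 3 or higher, serious, and Grade 2 or higher when the SRC judges it significant for the group. This brings 6.6.1.5 into line with 6.6.1.1 and the Table 7 note. No extra trigger is needed in 6.6.1.4, because a group suspension also stops the affected individual.

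The cost is one phrase in a protocol amendment. No test is added: bilirubin, GGT and ALP are already in Table 7, and liver enzymes are checked at least every 3 days.

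The downside is that one isolated, drug-related Grade 3 GGT or bilirubin reaction would suspend the group. That could interrupt the primary window, Days 4 to 15 (15 - 4 + 1 = 12 days), for everyone then dosing, and restarting would need an amendment approved by the MHRA and the ethics committee. Section 6.6.1.3 already accepts the same consequence for a Grade 3 reaction in other organs.

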#### **6.6.1.6. Safety Oversight and Implementation Stopping Rules**

- If one or more participants fulfill criteria from either the individual adverse reaction rules (outlined in Section 6.6.1.2 and/or Section 6.6.1.4) or for group adverse reaction rules (outlined in Section 6.6.1.3 and/or Section 6.6.1.5), a SRC meeting will be arranged. At this meeting, a decision will be made regarding the continuation/discontinuation of dosing for the remaining participants as well as need for dose modification. Based on the severity and medical risk to other participants and on request of either the Investigator or Alexion, dosing for all participants will be temporarily suspended until the SRC meets.
- The SRC will meet following completion of Day 18 of Group 1 to confirm adequate safety to complete dosing at 30 mg/day. Dose reduction to 15 mg/day may be made

following review of Group 1 data if there is evidence of over-decuppering as determined by AEs and/or ceruloplasmin concentration.

- The SRC will be comprised of, at minimum, the Investigator and Alexion's Medical Monitor. Additional site staff and Alexion personnel may also be included and will be responsible for reviewing all safety data and making determination around dosing.
- In the event of suspension of dosing, continuation of the study will require a protocol amendment that has been approved by the MHRA and ethics committee.

## **6.7. Intervention After the End of the Study**

This is a healthy participant study and no follow-up intervention is planned.

## 7. DISCONTINUATION OF STUDY INTERVENTION AND PARTICIPANT DISCONTINUATION/WITHDRAWAL

### 7.1. Discontinuation of Study Intervention

In rare instances, it may be necessary for a participant to permanently discontinue (definitive discontinuation) the study intervention. If the study intervention is definitively discontinued, the participant should remain in the study to be evaluated for safety follow-up. See the SoA for data to be collected at the time of discontinuation of study intervention and follow-up and for any further evaluations that need to be completed.

Discontinuation of study intervention for abnormal liver function should be considered by the investigator when a participant meets one of the conditions outlined in the Dose Modification criteria ([Section 6.6](#)) or if the Investigator believes that it is in best interest of the participant.

If a clinically significant finding is identified (including, but not limited to changes from baseline in QT interval corrected using Fridericia's formula [QTcF]) after enrollment, the Investigator or qualified designee will determine if the participant can continue in the study and if any change in participant management is needed. This review of the ECG printed at the time of collection must be documented. Any new clinically relevant finding should be reported as an AE.

Participants must be considered for discontinuation from intervention if any of the following occur during the study:

- Serious hypersensitivity reaction;
- Severe uncontrolled infection;
- Use of disallowed medication;
- Pregnancy or planned pregnancy (see [Section 8.2.6](#)); or
- Alexion or the Investigator deems it is necessary for the participant.

See the SoA ([Table 1](#)) for samples and data to be collected at the time of study intervention discontinuation and follow-up and for any further evaluations that need to be completed.

### 7.2. Participant Discontinuation/Withdrawal From the Study

- All efforts should be made to ensure participants are willing to comply with study participation prior to conducting the screening procedures. The study staff should notify Alexion and their site monitor of all study withdrawals as soon as possible. The reason for participant discontinuation must be recorded in the source documents and CRF.
- A participant may withdraw from the study at any time at his/her own request, or may be withdrawn at any time at the discretion of the Investigator for safety, behavioral, compliance, or administrative reasons. This is expected to be uncommon.
- At the time of discontinuation from the study, participants will be seen and assessed by the Investigator or study physician and whenever possible, will undergo the procedures associated with the early termination visit, as shown in the SoA. See the

SoA ([Section 1.3](#)) for data to be collected at the time of study discontinuation and follow-up and for any further evaluations that need to be completed.

- The participant will be permanently discontinued both from the study intervention and from the study at that time.
- If the participant withdraws consent for disclosure of future information, Alexion may retain and continue to use any data collected before such a withdrawal of consent.
- If a participant withdraws from the study, he/she may request destruction of any samples taken and not tested, and the Investigator must document this in the site study records.

### **7.3. Lost to Follow-up**

A participant will be considered lost to follow-up if he or she repeatedly fails to return for scheduled visits and is unable to be contacted by the study site.

The following actions must be taken if a participant fails to return to the clinic for a required study visit:

- The site must attempt to contact the participant and reschedule the missed visit as soon as possible and counsel the participant on the importance of maintaining the assigned visit schedule and ascertain whether or not the participant wishes to and/or should continue in the study.
- Before a participant is deemed lost to follow-up, the Investigator or designee must make every effort to regain contact with the participant (where possible, 3 telephone calls and, if necessary, a certified letter to the participant's last known mailing address or local equivalent methods). These contact attempts should be documented in the participant's medical record.
- Should the participant continue to be unreachable, he/she will be considered to have withdrawn from the study.

Discontinuation of specific sites or of the study as a whole are handled as part of [Section 10.1.8](#).

## 8. STUDY ASSESSMENTS AND PROCEDURES

- Study procedures and their timing are summarized in the SoA ([Section 1.3](#)). Protocol waivers or exemptions are not allowed.
- Immediate safety concerns should be discussed with Alexion immediately upon occurrence or awareness to determine if the participant should continue or discontinue study intervention.
- Adherence to the study design requirements, including those specified in the SoA, is essential and required for study conduct.
- All screening evaluations must be completed and reviewed to confirm that potential participants meet all eligibility criteria. The Investigator will maintain a screening log to record details of all participants screened and to confirm eligibility or record reasons for screening failure, as applicable.

